Patient Determined Disability Steps	Participant chooses one of 9 categories that describes their MS disability level.		X			X		X	X
MS Walking Scale-12	A 12-item self-report survey; measures the impact of MS on walking ability and daily activities over the past 2 weeks.		X	X	X	X	X	X	X
Godin Leisure-Time Exercise Questionnaire	4 questions; 7-day recall of leisure-time physical activity to determine if individual is already exercising at adequate levels.		X			X	X	X	X
Exercise Preparticipation Health Screening	Questionnaire about physical health to determine if medical consent to participate is required.		X						
Expanded Disability Status Scale	A 30-minute multiple item disease-specific instrument that characterizes disability level and determines disability progression in people with MS.			X			X		X
Timed 25 Foot Walk Test	Measure of walking speed; participant will perform twice. Only one trial must be in the eligibility range for inclusion (6 to 180 seconds). The time of both trials will be averaged for the outcome measure. Participants will be ineligible if physically unable to complete trial 2. If the assistive device/orthosis changes from pre- to post training, participants will be tested with the previous device.			X			X		X
6-Minute Walk Test	Measures the distance an individual can walk over a total of six minutes on a hard, flat surface. The goal is for the individual to walk as far as possible in six minutes. The individual can self-pace and rest as needed as they traverse back and forth along a marked walkway. If the assistive device/orthosis changes from pre- to post training, participants can choose device type, or no device at all.			X			X		X
Mini-Mental Status Exam	11-item test of cognitive impairment.			X					
Demographic survey/medication	Age; gender; type and history of MS; race/ethnicity; insurance status; living arrangements.				X	X	X	X	X
Short Assessment of Health Literacy-English (SAHL-E)	SAHL-E contains 18 items to assess an English-speaking adult's ability to read and understand common medical terms and estimate an adult's health literacy level.				X				
Neuro-QOL	A validated outcome measure of quality of life sponsored by the National Institute of Health recommended by the American Academy of Neurology.				X	X	X	X	X
Modified Fatigue Impact Scale-21	A 21-item self-report of the severity of fatigue and its effect on the participant's activities and lifestyle over the past 4 weeks.				X	X	X	X	X

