Multiple Sclerosis Impact Scale-29	A 29-item self-report of participant's views on the impact of MS on day-to-day life during the past two weeks.				X	X	X	X	X
Social Cognitive Battery	See Table 2.				X	X	X	X	X
Participant Feedback Survey	27-item survey obtaining participants' feedback with the exercise program to assist with program modification and post-study dissemination.					X			

Adherence log is maintained weekly by participant to evaluate fidelity of the intervention across groups, as well as measure adherence with the protocol.

Reason for group choice: If randomized to the choice group, the research coordinator will complete the Choice form, which asks questions to determine if the COVID pandemic influenced their decision-making process. If not administered at randomization, the Choice form will be completed at 16 weeks.

Table 2. Social Cognitive Theory Battery	
Tool	Description
Exercise Self Efficacy Scale⁷⁸	10-item Likert scale measuring an individual's self-efficacy to undertake exercise related tasks and overcome barriers related to exercising.
Exercise Goal Setting Scale⁷⁹	10-item Likert scale assessing the extent an individual sets exercise goals.
Multidimensional Outcome Expectancies for Exercise Scale⁸⁰	19-item Likert scale measuring an individual's beliefs or expectations about the benefits of regular exercise or physical activity.
Exercise Barriers	8 questions to measure an individual's beliefs about the barriers related to exercising.
Social Provisions Scale⁸²	6-item scale measuring the degree to which respondent's social relationships provide various dimensions of social support in relation to physical activity.
Physical Activity Self-Regulatory Scale⁸⁴	12-item scale measuring an individual's self-regulation in relation to exercise.
Barriers for Self-Efficacy	13-item scale measuring individual's self-efficacy to participate in exercise when encountering barriers.

Once all baseline outcome measures are obtained, participants will be randomized and notified soon after by the site research coordinator of their group assignment. Randomization completes enrollment.

COVID-19 Screening and Enrollment Procedures

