SA2: Evaluate and compare the effectiveness between participants randomized to their preferred delivery mode (TET(Choice) or FET (Choice)) and those who are not randomized to their preferred delivery mode (TET or FET). For this aim we will use the same models as the primary but examining and interaction term for Choice and treatment and contrasts will be conducted comparing the four cells. We will assess if the effect of Choice is the same for both treatments. Logistic regression will be used to assess the interaction between choice and adherence and attendance or dropouts. We also will examine time to dropout and/or time until dropout or poor compliance (which will be defined prior to final analyses). We also are interested in examining the intensity or compliance of the intervention to the choice as well as impact on the primary endpoint as noted above.

SA3: Evaluate changes in self-efficacy and adoption of exercise between these groups (TET, FET, TET(Choice), FET(Choice)). Self-efficacy and adoption of exercise are discussed above and use the same models and approach. We will also utilize mediation analyses to understand if the changes induced by exercise are mediated via the changes in self-efficacy. Here we will use the approach by MacKinnon built on Judd and Kenny.⁷⁹⁻⁸⁴ Analyses of the MSWS-12, MFIS, and the NeuroQOL will all be analyzed using regression models similar to the timed walk models above and will utilize the same contrasts for examining choice as well as treatment effects.

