- b. **Analysis plan for HTE.** There are two specific hypothesis driven analyses: (1) RRMS v PMS; we hypothesize that those with RRMS will do better than those with PMS regardless of group; this will be analyzed by adding an interaction term to the model shown in SA2 above where the interaction is between treatment effect and type of MS; (2) a) symptom management medications: participants may decrease symptom management medications due to a decrease in their symptoms. This would be viewed as a positive outcome; b) participants who change their disease modifying therapy (DMT) will do worse than those who do not change their DMT; again, an interaction of this with treatment effectiveness will be included in the model discussed under SA2 above. We are also interested in examining heterogeneity amongst key subgroups such as age, gender, etc. These are a byproduct of our sensitivity analyses but will inform the heterogeneity questions.
- c. **Basis for all HTE claims based on appropriate statistical contrasts among groups being compared, such as interaction tests or estimates of differences in treatment effect.** In addition to the interaction tests discussed above, we will also provide estimates of treatment effect for each such subgroup (e.g., RRMS, PMS) and the differences between the subgroups along with 95% confidence intervals (CIs). The addition of the effects plus CIs is to provide readers results that may be easier to interpret than the interaction terms in a regression – that is, the interaction tests and the treatment effect estimates are not competitive but supplement each other. Tests of whether the effects are different will also be made.
- d. **Plan to report all pre-specified analyses and, at a minimum, the number of post hoc analyses, including all subgroups and outcomes analyzed.** The process of measuring HTE, and all results, will be reported, including how subgroups were measured/defined (e.g., what counts as a change of medication), the total number of subgroups and the total number of outcomes tested. For all procedures, the bootstrap will be used for internal validation and p-value (and CI) adjustments will be presented using Bonferroni-type procedures.

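### Change of disease-modifying therapy is used as an effect modifier, although it can only be observed after randomisation

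*SAP*

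**What the plan says.** In the SAP section on heterogeneity of treatment effect (HTE), item b opens with "There are two specific hypothesis driven analyses". The second of these has two parts.

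- On symptom medication: "participants may decrease symptom management medications due to a decrease in their symptoms. This would be viewed as a positive outcome".
- On DMT: "participants who change their disease modifying therapy (DMT) will do worse than those who do not change their DMT", followed by "again, an interaction of this with treatment effectiveness will be included in the model discussed under SA2 above".

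The SA2 paragraph defines that model: "we will use the same models as the primary but examining and interaction term for Choice and treatment". Item c of the HTE section adds that "we will also provide estimates of treatment effect for each such subgroup", with differences between subgroups and 95% confidence intervals. Item d says the report will describe how subgroups were defined, including what was treated as a medication change. It also plans bootstrap validation and Bonferroni-type adjustment.

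In Protocol Table 1, the row "Demographic survey/medication" is marked at enrolment, 8 weeks, 16 weeks, 6 months and 12 months. At the end of the Enrollment section, the protocol states: "Once all baseline outcome measures are obtained, participants will be randomized".

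**The concern.** An effect modifier in a randomised comparison should be fixed before allocation. The other modifiers that the SAP names (type of MS, age, gender or sex, health literacy) meet that condition. DMT change does not. It may follow from worsening, which is what the walking outcomes measure, or from the delivery mode itself.

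Two results are then at risk. The contrast between changers and non-changers can come out as predicted with no effect of DMT change at all. The mode effects within subgroups compare people selected after allocation, so randomisation no longer protects them. A subgroup that cannot be identified at entry also cannot help a patient or clinician choose a mode. This matters because item a of the HTE section says subgroup heterogeneity may become very important for describing and recommending if non-inferiority is not shown.

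**Working it through.** The documents give no figure for this analysis, so there is nothing to reproduce. The check is of timing and model content, followed by an illustration.

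**1. Timing.** Detecting a change needs at least two medication records. Table 1 has one record before randomisation (enrolment) and four after it. Randomisation follows the baseline measures. Any change between scheduled records is therefore seen after allocation. The SAP does not itself say that the change occurs during the trial; this follows from the schedule.

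**2. Consistency within the item.** The symptom-medication part treats a change in medication as a result of symptom change, and so as an outcome. The DMT part, in the same item, treats a change in medication as a modifier. The SAP sets no time window, does not require the change to precede the outcome, does not separate reasons for change, and offers no method for a factor that depends on the outcome.

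**3. Where the term enters.** The non-inferiority test is the SA1 model, adjusted for site, age, gender and baseline EDSS (the protocol says EDSS or PDDS). DMT change is not in it. The term enters only the HTE extension of the SA2 model.

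**4. Illustration (all effect sizes and switching rates assumed).** Let Y be worsening in SD units and T the arm, allocated 1:1:

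- Y = δT + e, with e ~ N(0,1). There is no true effect modification, and DMT change has no effect on Y.
- logit P(change) = −2.2 + g·D. D is either early worsening, 0.7Y + 0.71u with u ~ N(0,1) (correlation with Y about 0.7), or Y itself.

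Large-sample values come from 4 million simulated subjects.

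*Same trigger in both arms:*

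| Driver of switching | g | Share changing (δ=0) | Changers minus non-changers (δ=0) | Mode effect when δ=0.30: non-changers / changers |
|---|---|---|---|---|
| Early worsening | 0.5 | 11% | 0.34 SD | 0.30 / 0.29 |
| Early worsening | 1.0 | 13% | 0.63 SD | 0.29 / 0.28 |
| Early worsening | 1.5 | 17% | 0.81 SD | 0.28 / 0.26 |
| Final outcome | 0.5 | 11% | 0.49 SD | 0.29 / 0.29 |
| Final outcome | 1.0 | 13% | 0.89 SD | 0.27 / 0.26 |

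With more switching (intercept −1.7, final outcome, g = 1.0, about 22% changers when δ=0.30) the last pair becomes 0.26 / 0.25. The spurious interaction is at most about 0.02 SD throughout.

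At N = 400 with early worsening and g = 1.0 (3,000 replicates, ordinary least squares, two-sided 5%), the changers-do-worse contrast is significant in 99% of trials. The interaction test rejects in 4.9% (δ=0) and 5.1% (δ=0.30).

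*Stronger trigger in one arm (early worsening, δ=0, no true modification):*

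| g in the two arms | Mode effect, non-changers | Mode effect, changers | Spurious interaction | Rejection at nominal 5%, N=400 |
|---|---|---|---|---|
| 0.5 and 1.0 | −0.05 | 0.23 | 0.28 SD | 16% |
| 0.5 and 1.5 | −0.10 | 0.37 | 0.47 SD | 37% |

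These rejection rates are for one unadjusted test.

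*Direction.* Take δ=0.30, switching driven by the final outcome, intercept −2.0, and g of 0.5 in one arm and 1.0 in the other. The mode effect among changers is then about 0.58 or −0.03, depending on which arm has the steeper slope. If g is 0.5 in both arms but switching is less common in the worse arm (log-odds lower by 0.7), both subgroups give about 0.32, slightly away from zero.

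**The case against.** A reader might infer that conditioning on DMT change pulls the mode difference towards zero and so favours the non-inferiority claim. The documents do not support this. The non-inferiority test is the SA1 model, which has no DMT-change term. The direction of bias is also not fixed: it is modestly towards zero with an identical trigger in both arms, and can go either way otherwise.

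A reader might also take the changers-do-worse result as assured by reverse causation. That worsening prompts a switch is a clinical possibility that the SAP neither states nor rules out, and no switching rate or reason for switching is given. The upper end of the illustration, near 0.9 SD, assumes that the final outcome itself drives switching. A trigger correlated 0.7 with it gives 0.34 to 0.63 SD for the same values of g.

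It could be added that testing a main-effect statement with an interaction is a separate fault. This is a weak point. A model with the interaction would ordinarily contain the main effect, and the item on relapsing versus progressive MS is worded in the same way.

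In the plan's defence, this is one secondary HTE item, with bootstrap validation, Bonferroni-type adjustment and a commitment to report how change was defined. That limits the severity. But these steps address overfitting, multiplicity and transparency; they do not address selection after randomisation. With an identical trigger the interaction test also keeps about 5% error, so the interaction is materially exposed only if reasons for switching differ by arm. Nothing in the plan would establish that they do not.

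**Conclusion.** The point stands as a flaw in a secondary analysis. DMT change is observed after randomisation and may result from worsening or from assigned mode. The contrast between changers and non-changers and the mode effects within those subgroups should therefore not be read causally or used to advise on mode at entry. The primary non-inferiority conclusion does not depend on it.

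The finding that DMT change is post-randomisation rests on Table 1 and the order of randomisation. The sizes rest wholly on assumption: about 0.3 to 0.9 SD for the changer contrast if worsening drives switching; little effect on the interaction if the trigger is the same in both arms; and 0.28 to 0.47 SD of spurious interaction, with 16% to 37% rejection at nominal 5%, under the unequal triggers tried. The SAP should be changed, but the validity of the main result is not at issue.

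**What to change.** 1. Remove the interaction of DMT change with treatment, and the mode effects by DMT-change subgroup, from the HTE models.
2. Use DMT status at baseline as the effect modifier, provided the enrolment form records it. This must be confirmed: the title of the Table 1 row mentions medication, but its description lists only demographic, insurance, living-arrangement and MS-history items.
3. Compare on-study DMT change between modes as an outcome, as the SAP already implies for symptom medication.
4. Label any comparison of changers with non-changers descriptive, and fix the definition and time window of a change before analysis.

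The cost is SAP wording and one check of the enrolment form; the design and visit schedule do not change. The loss is that the question about changers becomes descriptive only. If baseline DMT was not recorded, step 2 falls away and the SAP should say so.
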